4.2.16 Physical examinations

Physical examination data will not be summarized but will be listed only.

Any new finding(s) or aggravated existing finding(s), judged as clinically significant by the investigator or designee, will be reported as an AE.

4.2.17 Exploratory analyses

4.2.17.1 Annualised asthma exacerbation rate

Exacerbations experienced during the treatment period will be summarized descriptively for each treatment/weight group, including the number of exacerbations associated with an ED visit or hospitalization.

For the production of summary statistics, the AAER will be calculated using the time-based risk approach:

$$AAER = 365.25 * \text{Total number of exacerbations} / \text{Total duration of at risk on-treatment period (days)}$$

Summaries will also include the number of patients experiencing at least one exacerbation. Kaplan-Meier plots will be used to describe the time to first exacerbation

[figure not shown]
4.2.18 Subgroup Analysis

For the following data, descriptive summaries in Japan subgroup by treatment/weight group and overall will be presented:

- Disposition
- Demography and patient characteristics
- Study treatment
- PK
- PD
- FEV1
- ACQ-IA
- Global impression of change
- AEs
- Asthma exacerbation

5 INTERIM ANALYSES

CCI

6 CHANGES OF ANALYSIS FROM PROTOCOL

No change to the analysis stated in the CSP

8 APPENDIX

Appendix I Partial dates for AEs and prior/concomitant medication

▪ Adverse Events

- The missing day of onset of an AE will be set to:
 - First day of the month that the event occurred, if the onset YYYY-MM is after the YYYY-MM of first study treatment
 - The day of the first study treatment, if the onset YYYY-MM is the same as YYYY-MM of the first study treatment
 - The date of informed consent, if the onset YYYY-MM is before the YYYY-MM of the first treatment.
- The missing day of resolution of an AE will be set to:
 - The last day of the month of the occurrence. If the patient died in the same month, then set the imputed date as the death date.
- If the onset date of an AE is missing both the day and month, the onset date will be set to:
 - January 1 of the year of onset, if the onset year is after the year of the first study treatment.
 - The date of the first treatment, if the onset year is the same as the year of the first study treatment.
 - The date of informed consent, if the onset year is before the year of the first treatment.
- If the resolution date of an AE or end date of a IP is missing both the day and month, the date will be set to:
 - December 31 of the year of occurrence. If the patient died in the same year, then set the imputed date as the death date.

▪ Prior/concomitant medication

Dates missing the day or both the day and month of the year will adhere to the following conventions in order to classify prior/concomitant medications:

- The missing day of start date of a therapy will be set to the first day of the month that the event occurred.
- The missing day of end date of a therapy will be set to the last day of the month of the occurrence.
- If the start date of a therapy is missing both the day and month, the onset date will be set to January 1 of the year of onset.
- If the end date of a therapy is missing both the day and month, the date will be set to December 31 of the year of occurrence.

- If the start date of a therapy is null and the end date is not a complete date then the start date will be set to the date of the first study visit.
- If the start date of a therapy is null and the end date is a complete date:
 - and the end date is after the date of the first study visit then the start date will be set to the date of the first study visit.
 - otherwise the start date will be set to the end date of the therapy.
- If the end date of a therapy is null and the start date is not a complete date then the end date will be set to the date of the last study visit.
- If the end date of a therapy is null and the start date is a complete date:
 - and the start date is prior to the date of the last study visit then the end date will be set to the date of the last study visit.
 - otherwise, the end date will be set to the start date of the therapy.

SIGNATURE PAGE

This is a representation of an electronic record that was signed electronically and this page is the manifestation of the electronic signature

Document Name: d3250c00025-sap-ed-2			
Document Title:	d3250c00025-sap-ed-2		
Document ID:	CCI [REDACTED]		
Version Label:	1.0 CURRENT LATEST APPROVED		
Server Date (dd-MMM-yyyy HH:mm 'UTC'Z)	Signed by	Meaning of Signature	
19-Oct-2022 17:08 UTC	PPD [REDACTED]	Content Approval	
18-Oct-2022 14:53 UTC	PPD [REDACTED] QUINTILES	Author Approval	

CCI [REDACTED]

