3.3.6 Safety outcome variables

The following safety data will be collected: reported AEs (including SAEs), haematology, clinical chemistry, urinalysis, 12-lead electrocardiogram (ECG), physical examination and vital signs.

All safety measurements will use all available data for analyses, including data from unscheduled visits and repeated measurements.

Change from baseline to each post-treatment time point where scheduled assessments were made will be calculated for relevant measurements. AEs will be summarised by means of descriptive statistics and qualitative summaries.

No safety data will be imputed. The handling of partial/missing dates for AEs is detailed in [Appendix I](#).

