3.3.6.1 Adverse events (AEs)

Adverse events (including SAEs) experienced by the patients will be collected throughout the entire study and will be coded by the AstraZeneca designee using the latest version of the Medical Dictionary for Regulatory Activities (MedDRA).

Adverse event data will be categorized according to their onset date into the following study periods:

- AEs in the on-study period, defined as:

date of first dose of IP \leq AE onset date \leq study completion or withdrawal date.

- *AEs in the pre-treatment period (screening period) are defined as those with onset before the day of first dose of study treatment.* If any subject is re-screened, the latest available screening will be used for this purpose

If the AE has a completely missing (and unresolvable) onset date, then the AE will be assumed to be treatment-emergent, unless the end date indicates unambiguously that the AE resolved before treatment started. If the AE has a partially missing (and unresolvable) onset date, then the AE will also be assumed to be treatment-emergent, unless either the end date

indicates unambiguously that the AE resolved before treatment started, or the partial onset date is in the month/year prior to start of treatment.

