4.2.4 Study treatment

4.2.4.1 Exposure

Investigational product total treatment duration (days) is defined as the date of last dose minus the date of first dose plus 1 day.

Exposure to IP will be calculated in days as:

Exposure (days) =Last dose date of IP-first dose date of IP+1,

and will be summarized by treatment/weight group for the safety analysis set.

The date of all IP administrations, and all missed doses will be listed using the safety analysis set. Reason for missed dose will also be listed.

Exposure data will be summarised and listed for the safety analysis set.

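### SAP Appendix I can move an adverse event that ended before dosing onto the first-dose date, contrary to SAP 3.3.6.1

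*SAP*

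**What the plan says.** **Classification.** SAP 3.3.6.1 defines on-study AEs by "date of first dose of IP \leq AE onset date \leq study completion or withdrawal date" and adds that "AEs in the pre-treatment period (screening period) are defined as those with onset before the day of first dose of study treatment". For a partial and unresolvable onset date it assumes the AE is treatment-emergent, unless the recorded stop date of the AE "indicates unambiguously that the AE resolved before treatment started, or the partial onset date is in the month/year prior to start of treatment". SAP 4.2.12.1 assigns AEs and SAEs to the on-study period by onset date. Screening AEs are listed but not summarised separately.

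**Imputation.** SAP 3.3.6 states: "The handling of partial/missing dates for AEs is detailed in" Appendix I. SAP 3.1.5 points to the same place. Appendix I has two bullets that impute the first-dose date:

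- Day missing: "The day of the first study treatment, if the onset YYYY-MM is the same as YYYY-MM of the first study treatment".
- Day and month missing: "The date of the first treatment, if the onset year is the same as the year of the first study treatment".

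Neither bullet has a condition on the end date.

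**The concern.** The two parts of the SAP can give opposite answers for the same event. 3.3.6.1 uses a known end date to keep a resolved screening event out of the treatment-emergent AEs. Appendix I ignores that date, and the onset it supplies satisfies the on-study definition. Both pointers send the programmer to Appendix I, and no text says that 3.3.6.1 is applied first or overrides it. The labels do not help either: the exception speaks of treatment-emergent AEs, while the summary tables are built on on-study AEs.

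The result is also perverse. Appendix I has no rule for a completely missing AE onset, so 3.3.6.1 alone governs there and its end-date check applies. An event with no onset date at all is kept out, while one with a known onset month can be counted.

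Long-term safety is a stated aim of this small study, and AEs are collected from consent (Protocol 8.3.2). At stake is the attribution of pre-dose events to the benralizumab period, with dates that are impossible on their face.

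**Working it through.** The plan gives no figure to reproduce. The check applies both rules to the same events. The dates below are illustrative.

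**Inputs**
- First dose 20 March 2020; consent assumed 21 days earlier, 28 February 2020.
- Appendix I onset rules, followed by the on-study definition in 3.3.6.1.
- The partial-onset exception in 3.3.6.1, applied separately.

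| Known onset | End date | Appendix I onset | Appendix I plus on-study definition | 3.3.6.1 exception |
|---|---|---|---|---|
| March 2020 | 10 March | 20 March | On-study | Not treatment-emergent |
| 2020 only | 10 March | 20 March | On-study | Not treatment-emergent |
| March 2020 | 25 March | 20 March | On-study | Treatment-emergent |
| February 2020 | 10 March | 28 February | Pre-treatment | Not treatment-emergent |
| March 2020 | March only, imputed 31 March | 20 March | On-study | Treatment-emergent |

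The first two rows conflict, and the imputed onset falls 20 − 10 = 10 days after the event ended. The other three agree. In the last row a month-only end date in the first-dose month does not prove resolution before dosing, so the exception is not triggered.

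**How often the condition would be met, given a partial date.** Take AEs that start and end within L days of screening, with a complete end date and a missing onset day. All of them ended before dosing, so the rules disagree whenever the onset lies in the first-dose month. If k of the L screening days lie in that month, the share of onset/end pairs in conflict is k(k+1) / [L(L+1)]. Averaged over first-dose dates in a 30-day month this is [(L − 1)/3 + 30 − L] / 30:

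- L = 14: (4.33 + 16)/30 = 68%
- L = 21: (6.67 + 9)/30 = 52%
- L = 28: (9 + 2)/30 = 37%

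Enumerating every first-dose date in 2020–2021 on the real calendar gives 68%, 53% and 38%. For year-only onsets, replacing 30 by 365 gives 97%, 96% and 95%, and the enumeration agrees. These shares assume uniformly distributed dates and are conditional on a partial onset date. They are not expected counts.

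**Effect of one child.** SAP 1.3 plans 30 evaluable patients aged 6 to 11, with at least 8 per weight stratum. One child newly entering a row adds 1/30 = 3.3 points overall, or 1/8 = 12.5 points in a stratum of 8. Patient rows in 4.2.12.1 count a child once, so the change is zero if that child already has an event in the row. The separate event-count summary rises by one either way.

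**The case against.** The strongest reply is that the protection is already written down. Appendix I can be read as supplying date values and 3.3.6.1 as deciding classification, so a programmer who applies 3.3.6.1 first gets the right answer. That is a sensible reading, but the SAP does not state it. It would also still leave an onset later than the end date in the listing.

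The second reply is rarity, and it stands. SAP 3.1.5 anticipates missing dates only for concomitant medications, Protocol 8.3.4 collects the start and stop of each AE, and 3.3.6.1 concerns only unresolvable dates. A year-only onset with a usable pre-dose end date is hardly plausible within a screening period of about four weeks. The study is also descriptive, and the error does not touch the primary PK or PD endpoints.

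A reader might infer more from the same appendix, but the documents do not support it:

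- **Exposure.** The rule beginning "If the resolution date of an AE or end date of a IP is missing both the day and month, the date will be set" imputes 31 December, and one could suppose that this inflates "Last dose date of IP-first dose date of IP+1". But IP is given by the investigator or a delegate (Protocol 6.3.2), the last administration date is to be documented at discontinuation (Protocol 7.1.1), and all administration dates are listed (SAP 4.2.4.1). No realistic route to a year-only injection date is shown.
- **Medications.** A therapy with no start date and a partial end date years earlier is given the first study visit as its start. The date is odd, but the imputed stop date still precedes dosing, so the therapy remains prior under SAP 4.2.3.1.

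**Conclusion.** The contradiction holds. Programmed as written, Appendix I counts some AEs known to have ended before dosing as on-study, with an impossible sequence of dates, where 3.3.6.1 would exclude them. This is a stated rule that gives a wrong result, not merely a missing detail.

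Three conditions must coincide: a partial onset date, a match with the first-dose month (or year, if only the year is known), and an end date that shows resolution before dosing. The number of such AEs cannot be known from the documents and is probably small.

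It would be wrong to infer that most screening AEs are miscounted, since the shares above apply only once the onset date is already partial. Nor does every affected AE add 3.3 or 12.5 points. Those are upper limits for one child with no other event in the row, and they use planned numbers. The 8 is a minimum of evaluable patients, so a larger safety set makes the effect smaller. The SAP also plans AE summaries for a Japan subgroup (4.2.18), whose size the documents do not give.

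**What to change.** Add to both first-dose-date onset bullets in Appendix I:

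*unless the end date shows without ambiguity that the event was over before the first dose; the AE is then classed as pre-treatment, and its onset is set to the later of the informed consent date and the first day of the known onset month (the consent date if only the year is known).*

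In the year-only case, if consent fell in the previous calendar year, 1 January of the known year keeps the imputed date within that year.

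Also state that no imputed onset may fall after a known end date, and that 3.3.6.1 governs classification, including for the on-study summaries. In the example above, the month-only event would get an onset of 1 March and the year-only event 28 February. Both precede the 10 March end date and are pre-treatment.

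The cost is a few lines of SAP text and a small programming change, with no new data and no real downside. Nothing here requires a change to the IP end-date or therapy start-date rules.
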